| 2 | When Informed consent has been obtained all adverse events must be reported in the eCRF |
| 3 | For practical purposes, when dispensing trial drug, the body weight from an earlier measurement (or visit) can be used if the measurement was performed within the previous 12 weeks (in children < 3 years of age, within 6 weeks). After visit 29, a body weight measured within the previous 12 weeks for all age groups can be used. Please refer to Section 8.3.1 . |
| 4 | Vital signs should be measured prior to dosing at screening, V1, V23, V28 and EOT. In addition vital signs should also be measured 30±10 minutes after the first injection with N9-GP at V1 |
| 5 | FIX activity should only be measured at V0 if diagnosis of haemophilia B (FIX≤2%) has not been documented in the patients' medical record. FIX activity at V0 can either be measured at local or central laboratory depending on the urgency of receiving the result i.e. in case V0 and V1 are combined |
| 6 | FIX recovery activity is measured 30 min ±10 min after dosing at the following EDs: 1, 10, 20, 50 and 100. For details please refer to Section 8.4.2.1 |
| 7 | Blood samples must be collected within 1 hour prior to dosing at dosing visits |
| 8 | HIV antibodies are only to be assessed, if status is unknown (i.e. previous test older than 6 months). Tests for CD4+ lymphocyte count and HIV viral load are only required for HIV positive patients. Sampling can be postponed to the earliest convenient visit to ensure that the allowed blood volume is not exceeded |
| 9 | In case V1 is more than a month after V0, haematology and biochemistry need to be retaken at V1 prior to dosing. Biochemistry also needs to be retaken at visit 1 if biochemistry at V0 was a local assessment. Please refer to Section 8.4.2.4 and 8.4.2.5 |
| 10 | F9 and HLA genotype sample should be taken prior to administering the first dose of N9-GP or at a visit as soon as possible thereafter taking the limitation of the allowed blood sampling volume into account. |
| 11 | eDiary training prior to initiating home treatment to ensure that the patient's parent(s)/LAR(s) are comfortable entering data in the eDiary. Retrain in the use of the eDiary as applicable at V21-VX to ensure entry of correct eDiary data |

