Serious and non-serious adverse events (AE) from screening failures must be transcribed by the investigator into the case report form (eCRF). Follow-up of SAEs must be carried out according to Section [11.3](#). A screening failure session must be made in the IWRS. The case book must be signed.

Re-screening is **not** allowed after the first dose of trial product – see excl. criteria no. 2 in Section [6.3](#).

For withdrawn patients

Withdrawn patients are defined as patients who meet the withdrawal criteria after dosing, see Section [6.4](#)

If a patient is withdrawn from the trial, the investigator must aim to perform the end of trial visit, as soon as possible except for patients with a high titre inhibitor.

The end of trial form must be completed, and final drug accountability must be performed even if the patient is not able to come to the trial site. A withdrawal session must be made in the IWRS and the case book must be signed.

All data collected in the period the patient participated in the trial must be documented.

Although a patient or patient's parent(s)/LAR(s) is not obliged to give his/her reason(s) for withdrawing from a trial, the investigator must make a reasonable effort to ascertain the reason(s),

Protocol
 Trial ID: NN7999-3895
 UTN: U1111-1135-9557
 EudraCT No.: 2012-004867-38

~~CONFIDENTIAL~~

| | | |
|----------|------------------|---------------------|
| Date: | 05 November 2019 | Novo Nordisk |
| Version: | 8.0 | |
| Status: | Final | |
| Page: | 37 of 119 | |

while fully respecting the patient's rights. Where the reasons are obtained, the primary reason(s) for discontinuation must be specified on the end-of-trial form in the eCRF e.g.:

- Adverse events (AEs)
- Protocol violation
- Lack of efficacy
- Lost to follow up
- Withdrawal by patient or parent(s)/LAR(s)
- Technical problems
- Other

End of trial

The end of trial (EOT) form should be filled in at the End-of-Trial visit or the last visit of the patient. If a patient is withdrawn prior to completion of the trial, all attempts must be made to schedule the end of trial visit for the patient.

For a patient with high titre inhibitor the EOT visit should be performed in connection with the third follow-up visit.

In general

Review of eDiary reports, laboratory reports etc. must be documented either on the front page of the documents and/or in the patient's medical record.

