8.1.1 Visit 0 – screening visit

The patient's parent(s)/LAR(s) must give signed and dated informed consent prior to any trial related activities. Signing of the informed consent can take place before visit 0, if allowed by local

Protocol
 Trial ID: NN7999-3895
 UTN: U1111-1135-9557
 EudraCT No.: 2012-004867-38

~~CONFIDENTIAL~~

| | | |
|----------|------------------|---------------------|
| Date: | 05 November 2019 | Novo Nordisk |
| Version: | 8.0 | |
| Status: | Final | |
| Page: | 38 of 119 | |

law. All patients will be provided with a copy on the patient information and a copy of the signed and dated Informed Consent Form.

For all patients with a signed Informed Consent/Assent form, the patient will be assigned a unique 6 digits patient number, which will follow the patient throughout the trial.

A screening period (interval between visit 0 (V0) and V1) is allowed until the first dose of N9-GP is required.

The screening visit (V0) can be combined with the first treatment of N9-GP (V1), hereby allowing patients to be enrolled in the trial and treated for their first bleeding episode immediately after having confirmed inclusion and exclusion criteria.

All results necessary for evaluating the inclusion and exclusion criteria must be available before determining whether or not the patient can continue in the trial and whether it will be possible to receive the first dose of N9-GP at the same day.

If the screening results do not become available during the screening visit, and if the next visit is not planned, the patient's parent(s)/LAR(s) must be informed when eligibility has been evaluated by the investigator.

Assessments for V0 are listed in [Table 2-1](#).

Reminders:

- Dispense trial card, see Section [8.8.1](#)
- Screening call in the IWRS, see Section [10](#)
- Discuss treatment regimen: prophylaxis versus pre-prophylaxis
- In case V1 is not planned or performed within 3 month from visit 0 the investigator must contact the patient's parent(s)/LAR(s) at least every 12 weeks \pm 1 week, See Sections [8.8.4](#) and [8.1.10](#).
- During the screening period the patient cannot be treated with commercially available FIX product

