8.2 Patient related information

8.2.1 Concomitant illness and medical history

A **concomitant illness** is any illness that is present at the start of the trial at the first visit, (V0) or found as a result of a screening procedure. All concomitant illnesses should be reported including the disease under investigation.

Medical history is a medical event that the patient has experienced in the past, which should be obtained during the screening procedure including haemophilia treatment history. In the event that a diagnosis is unknown, the description of symptoms will be recorded. All significant symptoms and/or illnesses since births should be recorded.

The information collected for concomitant illness and medical history should include diagnosis, date of onset and date of resolution or continuation, as applicable.

Any change to a concomitant illness should be recorded during the trial. A clinically significant worsening of a concomitant illness must be reported as an AE.

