11.2 Reporting of adverse events

All events meeting the definition of an AE must be collected and reported. This includes events from the first trial-related activity after the patient's parent(s)/LAR(s) has signed the informed consent until the end of the trial. The events must be recorded in the applicable CRF forms in a timely manner. See timelines below.

Protocol
 Trial ID: NN7999-3895
 UTN: U1111-1135-9557
 EudraCT No.: 2012-004867-38

~~CONFIDENTIAL~~

| | | |
|----------|------------------|---------------------|
| Date: | 05 November 2019 | Novo Nordisk |
| Version: | 8.0 | |
| Status: | Final | |
| Page: | 84 of 119 | |

AEs experienced after signing of informed consent and before first dosing should only be reported if associated with trial related activities.

During each contact with the trial site staff (trial site visits and telephone contacts) the patient and/or patient's parent(s)/LAR(s) must be asked about AEs and technical complaints, e.g. "Have your child experience any problems since the last contact?"

All AEs, either observed by the investigator or reported by the patient, must be reported by the investigator and evaluated. Novo Nordisk assessment of expectedness is performed according to the following reference documents: Investigator's Brochure⁷, N9-GP, current version and any updates thereto.

For Japan only: If obtaining marketing approval in Japan, sponsor's assessment of expectedness is done according to the package insert of the commercial products in Japan.

All AEs must be recorded by the investigator on an AE form. The investigator should report the diagnosis, if available. If no diagnosis is available, the investigator should record each sign and symptom as an individual AE using separate AE forms.

For each SAE and MESI an electronic Safety Information Form (eSIF) should be completed in addition to the AE form in the eCRF. If several symptoms or diagnoses occur as part of the same clinical picture, one SIF may be used to describe all the SAEs. All concerned AE numbers must be included in the AE number field on the SIF.

MESIs, regardless of seriousness, must be reported using both the AE form and the safety information form. For MESIs of allergic aetiology, the hypersensitivity questionnaire must be completed.

The AE form for a non-serious AE should be signed when the event is resolved or at the end of the trial.

Timelines for initial reporting of AEs:

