The investigator must ensure that the worst case severity and seriousness of an event is kept throughout the trial. A worsening of an unresolved AE must be reported as follow up with re-assessment of severity and/or seriousness of the event.

Queries or follow-up requests from Novo Nordisk must be responded to **within 14 calendar days** from the date of receipt of the request, unless otherwise specified in the follow-up request.

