16.4.2.5 Safety endpoints

Adverse events including SAEs, MESI and development of HCP antibodies

Treatment emergent AEs (TEAEs, defined as AEs occurring after dosing with trial product) and treatment emergent SAEs (TESAEs) will be summarised by frequency of events and frequency of patients with any event. Similar summaries cross-classified by severity and by causal relation to trial product will also be made.

MESIs will be summarised similarly to AEs.

Furthermore, listings will be provided displaying all TEAEs and TESAEs including pertinent clinical information.

HCP antibodies will be listed.

Protocol
 Trial ID: NN7999-3895
 UTN: U1111-1135-9557
 EudraCT No.: 2012-004867-38

~~CONFIDENTIAL~~

| | | |
|----------|------------------|---------------------|
| Date: | 05 November 2019 | Novo Nordisk |
| Version: | 8.0 | |
| Status: | Final | |
| Page: | 100 of 119 | |

All additional safety parameters such as laboratory parameters, including calculation of estimated glomerular filtration rate (eGFR), and physical examinations, including neurological assessments, will be summarised and listed.

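### The protocol gives contradictory rules for recording AEs between consent and first dose, and its TEAE definition leaves out a recorded pre-dose AE that worsens on treatment

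*Protocol*

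**What the plan says.** **All AEs from consent.** Protocol Table 2–2, footnote 2: "When Informed consent has been obtained all adverse events must be reported in the eCRF". Section 11.2 opens in the same sense: "All events meeting the definition of an AE must be collected and reported", counted from the first trial-related activity after consent. Section 8.1 adds, for children who are never dosed: "Serious and non-serious adverse events (AE) from screening failures must be transcribed by the investigator into the case report form (eCRF"). None of the three asks whether the event is related to trial activities. Table 2–1 also marks AE collection at V0.

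**Only some AEs before dosing.** Later in Section 11.2: "AEs experienced after signing of informed consent and before first dosing should only be reported if associated with trial related activities".

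**Length of the window.** Section 8.1.1: "A screening period (interval between visit 0 (V0) and V1) is allowed until the first dose of N9-GP is required". No maximum is given. If V1 is more than three months away, the site must make contact about every 12 weeks, and Section 8.8.4 has that contact ask about all AEs. V0 and V1 may also be combined, in which case there is no window.

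**Illness already present.** Section 8.2.1 defines a concomitant illness as "any illness that is present at the start of the trial at the first visit, (V0"), or one found by a screening procedure. Sections 8.2.1 and 11.1 make a clinically significant worsening of a concomitant illness an AE.

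**Worsening of an AE already on file.** Section 11.3: "A worsening of an unresolved AE must be reported as follow up", with severity and seriousness re-assessed.

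**What is tabulated.** Section 16.4.2.5: "Treatment emergent AEs (TEAEs, defined as AEs occurring after dosing with trial product"). TEAEs and TESAEs are summarised and listed, and MESIs are summarised in the same way. The SAP covers only the neurocognitive data (SAP Section 6) and gives no other definition.

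**The concern.** Two instructions in force at the same time tell a site to do different things with an ordinary childhood illness in the screening interval. Footnote 2 has it recorded. The later sentence of Section 11.2 has it left out unless it is tied to a trial activity. Section 11.2 thereby contradicts its own first paragraph. It also means that a screening failure's pre-dose AEs are recorded more fully than those of a child who goes on to be treated.

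AEs, SAEs and MESIs are key supportive secondary endpoints (Section 4.2.2) of a single-arm trial, so no control group would share a recording artefact. MESIs include developmental, cognitive, behavioural and renal events (Section 11.1), which are followed because of a theoretical concern about PEG (Section 3.4). Such conditions can emerge gradually in young children, so an onset before dosing with progression afterwards is plausible. What is at stake is whether the planned tables show that progression, and whether they do so in the same way at every site.

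**Working it through.** The plan states no figure on this point, so the check is to run the rules on cases.

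**Step 1: onset before the first dose, no later change.** Under footnote 2 it is an AE with pre-dose onset. Section 16.4.2.5 counts AEs occurring after dosing, so it is not a TEAE. Under the Section 11.2 restriction it is not recorded, so it is not a TEAE either. Its contribution to the TEAE count is 0 under both rules. Only the presence of a pre-dose record differs.

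**Step 2: the same illness is unresolved at first dose and worsens afterwards.** Assume that it is unrelated to trial activities and was not found by a screening procedure.

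| Start of illness and rule followed | Record before first dose | Status of the post-dose worsening | Counted as TEAE? |
|---|---|---|---|
| After V0, footnote 2 | Open AE, pre-dose onset | Follow-up of that AE (11.3) | No |
| After V0, 11.2 restriction | None | May be entered as a new AE | Yes, if so entered |
| Present at V0 | Concomitant illness | AE if clinically significant (8.2.1, 11.1) | Yes |

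The same clinical course therefore has different outcomes in the tables. The first row is the one that loses information. Section 11.3 treats even a change from non-serious to serious as follow-up, so the event would be missing from the TESAE table too, and from the MESI summary if that follows the same convention.

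**Step 3: what the table rests on.** It reads *occurring* in Section 16.4.2.5 as onset, which is the natural reading. The second row is an inference, because no passage says what a site should do with an illness that was never recorded and then flares.

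**Step 4: size.** The quantity needed is the number of children whose recorded pre-dose AE was open at first dose and then worsened. The documents give no AE rate, no distribution of the V0–V1 interval and no probability of worsening, so it cannot be calculated.

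**The case against.** The other side has several sound points.

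- **Onset alone.** A reader might infer that any illness starting between V0 and first dose is a TEAE under one rule and not under the other. Step 1 shows that this is wrong.
- **Inflation.** A reader might infer that the Section 11.2 route inflates TEAE counts. It does not: a worsening that appears on treatment is what a TEAE table should show, and the fix below counts it. The faulty route is the one that omits it.
- **Size.** It is tempting to size the problem by the pre-dose AEs recorded under one rule and not the other. Assuming a mean V0–V1 interval of 1 to 6 months and 3 to 6 AEs per patient-year, 60 patients would give 60 × (1/12) × 3 = 15 to 60 × (6/12) × 6 = 180. Both inputs are assumptions, and the result counts pre-dose AEs, which the TEAE tables exclude anyway. It says nothing about how many are misclassified.
- **Surveillance.** A reader might infer that on-treatment deterioration is hidden from the sponsor. Section 11.3 requires re-assessment and 24-hour reporting when an AE becomes serious, and Section 11.6.1 requires post-dose events meeting SAE or MESI criteria to be reported. The gap is in the planned summaries and listings only.
- **Rarity.** The follow-up rule applies only to unresolved AEs, so a resolved illness that recurs is outside it. Section 8.1.2 has the first dose postponed where possible after recent signs of illness or fever, which makes an acute illness still open at first dose less common. Where V0 and V1 are combined the case cannot arise.

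These points narrow the consequence. They do not reconcile the passages, and they leave the first row of the table standing.

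**Conclusion.** The contradiction is real, and both rules cannot be followed. Its effect on the analysis is narrow: an illness that starts after V0, is recorded under footnote 2, is still open at first dose and worsens on treatment drops out of the TEAE summaries, and out of the TESAE summaries if it becomes serious. The same worsening of an illness present at V0 is counted, and that of an unrecorded illness may be.

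The number of children affected is unknown and probably small. The primary endpoint (FIX inhibitors), AEs with onset after dosing and individual SAE/MESI reporting are not affected. The conclusion rests on reading the TEAE definition by onset and on the absence of any other definition in either document. It merits correction because the endpoints concerned are key secondary safety endpoints and the change is cheap.

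**What to change.** 1. State one pre-dose recording rule in Table 2–2, footnote 2, and in Section 11.2. The better choice is all AEs from consent, with those starting before the first dose flagged as pre-treatment. This matches the opening of Section 11.2 and the screening-failure text.
2. In Section 16.4.2.5, define a TEAE as an AE with onset after the first dose, or a pre-dose AE or illness that worsens in severity or seriousness after the first dose. Apply the same definition to TESAEs and MESIs.
3. In Section 11.3, have the date of worsening captured, either as a new AE or as a dated follow-up entry, so that it can be counted.
4. Apply the rule from the amendment onward and describe the change in the report. Version 8.0 is dated 5 November 2019, about 64 months after the first patient's first visit (2 July 2014) in a planned 75-month recruitment. Pre-dose events in children already dosed cannot be collected prospectively, and the report should say that collection rules differed over time.

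The cost is a few sentences of protocol text, a few extra AE forms for the screening interval and slightly higher TEAE counts.

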3.1 Background information

Haemophilia B is a recessive X-linked congenital bleeding disorder characterised by increased bleeding tendency due to either a partial or complete deficiency or dysfunction of the essential blood coagulation factor IX (FIX). It is caused by mutations in the *F9* gene, located in the distal part on the long arm of the X-chromosome. The incidence of haemophilia B is approximately 1 per 25,000 male births. Haemophilia care is based on prevention (prophylaxis) and/or “on-demand treatment” of bleeding episodes with a haemostatic agent.

With a deficiency or absence of FIX, activation of coagulation factor X (FX) becomes severely impaired, and consequently, the thrombin burst becomes delayed and insufficient for normal haemostasis. The haemostatic plug formed in these patients is therefore fragile and easily dissolved by normal fibrinolytic activity, leading to impaired haemostasis, prolonged bleeding and rebleeding³. Haemophilia B is classified according to the plasma activity of FIX as severe (<1%), moderate (1-5%) or mild (>5-40%).

The predominant treatment for patients with haemophilia B is factor replacement therapy where concentrates of FIX are injected intravenously to replace the deficient and/or dysfunctional FIX. Haemophilia care is based on treatment of a bleeding episode with a haemostatic agent or - during recent decades - haemostatic agents are administered for longer periods to prevent bleeding (bleeding prophylaxis).

The most commonly used products for the treatment of haemophilia B are plasma derived FIX and recombinant FIX (rFIX). Both have half-lives of 18-19 hours requiring 2-3 weekly injections for prophylaxis of bleeding episodes.⁴

The clinical manifestations of haemophilia B are bleeding episodes due to impaired haemostasis. The bleeding episodes in patients with severe haemophilia B typically occur spontaneously or after mild trauma in joints, muscles and soft tissues. The bleeding episodes often occur in muscles and weight bearing joints (elbows, knees and ankles), causing acute haemarthrosis. In repeated cases this is followed by synovitis in the affected joint. Recurrent bleeding episodes in the same location, most commonly a weight-bearing joint, may lead to chronic arthropathy, muscular atrophy and disabling deformities. Bleeding may occur in all parts of the body including rare, but life-

Protocol
 Trial ID: NN7999-3895
 UTN: U1111-1135-9557
 EudraCT No.: 2012-004867-38

~~CONFIDENTIAL~~

| | | |
|----------|------------------|---------------------|
| Date: | 05 November 2019 | Novo Nordisk |
| Version: | 8.0 | |
| Status: | Final | |
| Page: | 20 of 119 | |

threatening events such as: e.g. bleeding in the central nervous system (CNS), throat, neck or retroperitoneum.

3.2 Rationale for the trial

The rationale for performing this trial is to investigate safety and efficacy of N9-GP in the treatment of previously untreated patients (PUP) with haemophilia B, hereby supporting anticipated marketing authorisation of N9-GP and line extension in the PUP population.

EMA requires separate investigation of PUPs as part of the development programme initiated before market authorisation (MA) gets obtained. A final guideline on the clinical investigation of recombinant and human plasma-derived factor IX products⁵ from the Committee for Medical Product for Human Use (CHMP), describes the mandatory components for trials in PUP. In some countries outside the EU, PUP Paediatric investigation is necessary to achieve labelled indication for all children.

